	
household contact IGRA positivity between aTB-C and sTB-C index cases is 0.90, 150 index cases of each TB phenotype in each setting will give us $\geq 80\%$ power to demonstrate that the transmission risk with aTB-C is not less than 50% of the transmission risk of sTB-C.
 
The index adults from the 600 households in each setting will be enrolled in the case-control phenotyping study. Assuming that the true sensitivity and specificity of the diagnostic tools are between 70-95%, with 150 aTB-C and 150 sTB-C cases, we will be able to estimate the sensitivity with a precision of $\pm 7.6\%$ to $\pm 4\%$. With 300 controls, we will be able to estimate the specificity with a precision of $\pm 5.3\%$ to $\pm 2.6\%$.
 
In each setting, after community screening, we expect to identify 500 participants with aTB-U who are eligible for the TB-U cohort. Based on the assumed annual progression rate, this sample size is expected to yield 31-66 individuals with progressive disease. With 50 individuals who progress and 100 who do not, we will have $\geq 80\%$ power to detect a difference of 0.50 standard deviations in mean biomarker concentrations between the two groups. If the prevalence of biomarkers in individuals who do not progress is 10-20%, we would have $\geq 80\%$ power to detect an increase to 30-40%.

Study Population	
Cross-sectional study of household Mtb infection (core study)
 
 • Community screening: Adolescents and adults (≥ 15 years) who reside in households with children 2-14 years and located within the study areas in each setting. • Child contacts: Children (2-14 years) who are household contacts of participants with aTB-C, sTB-C, or of randomly selected neighbourhood households with adults without TB 
Case-control phenotyping study (sub-study 1) Adolescents and adults (≥ 15 years) who were identified through community TB screening to have aTB-C, sTB-C and no TB
 
Cohort (sub-study 2) Adolescents and adults (≥ 15 years) who were identified through community TB screening with bacteriologically-unconfirmed TB (TB-U)

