5. STATISTICAL CONSIDERATIONS AND MODELLING

5.1 SAMPLE SIZE CALCULATIONS

CORE STUDY

The core study has two co-primary objectives: (1) to compare IGRA positivity in child household contacts of participants with aTB-C with that of community controls; (2) to compare IGRA positivity in child household contacts of participants with aTB-C cases with that of participants with sTB-c. We are using child IGRA positivity as a proxy measure of TB transmission.

Based on our existing data on the prevalence of aTB-C in each setting, we expect to screen 60,000 individuals in Bandung and 30,000 in KwaZulu Natal to identify 150 cases of aTB (**Table 3**). We expect ~20% of children to be IGRA positive in control households in Bandung and 7% to be positive in KwaZulu Natal, and an average of 1.5 (SD=0.7) and 2.5 (SD=1.6) children per household, respectively, in each setting. We have assumed an intra-cluster correlation coefficient (ICC) of 0.20-0.30 in each setting, based on our data in KwaZulu Natal⁶⁴.

Table 3: Assumptions used to determine overall scale of screening and power for the asymptomatic TB transmission in Indonesia and South Africa study

Parameter	Indonesia	South Africa
Number screened	60,000	30,000
Asymptomatic TB prevalence (Clinical -, CXR positive, micro +/-)	0.25%	0.50%
Number of asymptomatic TB cases detected	150	150
Number of control HH	300	300

IGRA positivity in children aged 2-14 years	STB index HH: 40% Control HH: 20%	STB index HH: 18% Control HH: 7%
Household size (children aged 2-14 years)	Mean = 1.5 SD = 0.7	Mean = 2.5 SD = 1.6
Intra cluster correlation (ICC)	0.20 to 0.30	0.20 to 0.30

For our first co-primary objective, we have used the absolute risk difference in child IGRA positivity (rather than the risk ratio) as our effect estimate of interest, because of the difference in duration of exposure (lifetime exposure to community transmission for children in control households, vs a relatively short duration of exposure to the index case for children in aTB-C households).

If the true risk difference between IGRA positivity in aTB-C households compared to control households is 10-15%, inclusion of 150 aTB-C households and 300 control households will provide $\geq 90\%$ power to detect a significant difference in household IGRA positivity between these groups. We will have 80% power to detect a minimum difference of 12% in Bandung and 7% in KwaZulu Natal ([Table 4](#)).

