Table 4: Minimum risk difference that can be detected in each site with 80% power, comparing aTB and control households

Number aTB cases	Number controls ¹	Mean children per HH	ICC	% IGRA positive in control HH	% IGRA positive in aTB HH	Risk difference ²	Power
Indonesia							
150	300	1.5	0.30	20%	32%	12%	80%
South Africa							
150	300	2.5	0.30	7%	14%	7%	80%

¹Number of control households. ²Absolute difference = proportion of children IGRA+ in aTB households minus proportion of children IGRA+ in control.

For our second co-primary objective, we have used the risk ratio (relative risk) as the effect estimate of interest, because the duration of exposure for children in aTB-C and sTB-C households is expected to be similar. For policy decisions, it would be useful to know that the transmission risk of aTB-C is not substantially lower than that of sTB-C; therefore, we have used a non-inferiority approach for our power calculations. We have assumed that the prevalence of IGRA positivity in children in sTB-C households is 40% in Bandung and 18% in KwaZulu Natal (our best estimates, based on available data). With 150 sTB-C and 150 aTB-C index cases, we will have at least 80% power in each setting to demonstrate that the transmission risk with aTB-C is not less than 50% compared with that of sTB-C, assuming that the true risk ratio (RR) is at least 0.90 ([Table 5](#)).

Table 5: Relative reduction that can be excluded with 80% power, comparing aTB and sTB households¹

Number sTB cases	Number aTB cases	% IGRA positive in sTB HH	% IGRA positive in aTB HH	Risk ratio (aTB/sTB)	Relative reduction that can be excluded ²
Indonesia - aTB vs sTB					
150	150	40%	28%	0.70	0.46
150	150	40%	32%	0.80	0.55
150	150	40%	36%	0.90	0.63
South Africa - aTB vs sTB					
150	150	18%	12.6%	0.70	0.43
150	150	18%	14.4%	0.80	0.49
150	150	18%	16.2%	0.90	0.55

¹Assuming ICC=0.30. ²Lower limit of 95% confidence interval for risk ratio

CASE-CONTROL STUDY (SUB-STUDY 1)

The case-control study will enrol 150 aTB-C and 150 sTB-C cases, and 300 community controls with no TB. Assuming that the true sensitivity and specificity of the Plus Life tongue swab and bioaerosol collection facemask diagnostic tools are between 70-95%, with 150 aTB-C and 150 sTB-C cases, we will be able to estimate the sensitivity with a precision of $\pm 7.6\%$ to $\pm 4.0\%$. With 300 controls, we will be able to estimate the specificity with a precision of $\pm 5.3\%$ to $\pm 2.6\%$.

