5.2 ANALYTICAL APPROACH

Descriptive statistics will be used to summarise participant characteristics separately for each study setting, including household-level characteristics (e.g. socioeconomic status, household construction, number of household members), index-case level characteristics (e.g. age, sex) and child-level characteristics. The analyses for each endpoint will be conducted separately for each setting.

CORE STUDY

Comparison of aTB and control households: For the primary analysis, we will use random-effects logistic regression with a fixed effect for exposure group (aTB vs control) and a random intercept for household. Since control houses will be selected from the same neighbourhood as the aTB index cases, we will also include a random effect for matched set. From the fitted model, we will estimate the marginal risk difference in the proportion IGRA positive between the two groups.

Matching on neighbourhood will provide some control of confounding by neighbourhood-level factors (e.g. socioeconomic status, background exposure in the community). However, we will also conduct multivariable analyses, explicitly controlling for confounding using child-level (e.g. age, sex and degree of contact with index, such as sleeping in same room etc) and household-level covariates (e.g. household crowding). Covariate adjustment will be guided by theoretical causal diagrams, defined *a priori*.

Comparison of aTB and sTB households: For the primary analysis, we will use random-effects logistic regression with a fixed effect for TB exposure group (aTB vs sTB) and a random intercept for household. The marginal risk ratio will be estimated from the fitted model.

We will also conduct multivariable analyses, controlling for confounding using child-level, index case-level (age, sex, HIV status) and household-level covariates, as described above, with covariate adjustment guided by theoretical causal diagrams, defined *a priori*. If there is evidence of a difference in the infectiousness of aTB compared with sTB we will explore whether this is mediated through characteristics of index case disease severity (bacillary burden, cavitation etc) or other mechanisms.

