Sensitivity analyses: In a high TB incidence setting, IGRA positivity in household members may be result of contact with infected individuals outside the household, rather than with the index case. This would lead to outcome misclassification since the assumption underlying our analysis is that IGRA-positivity is

a result of exposure to the index case. This effect should be non-differential so would bias estimates towards the null. We will conduct sensitivity analyses restricted to younger children (e.g. aged <10 years), with the assumption that younger children are more likely to have been infected by the household index case than through community or non-household contact. Additionally, quantitative bias analyses will be performed using alternate definitions of 'asymptomatic' and 'symptomatic' TB-C index cases to account for 'misclassification' between these groups based on discrepancies between W4SS status at screening and the additional blinded symptom data collected at Visit 1.1.

CASE CONTROL STUDY (SUB-STUDY 1)

We will assess the performance of the standard and novel tools for diagnosing aTB-C and sTB-C by calculating the sensitivity, specificity, PPV, NPV and yield, and 95% confidence intervals, of each tool. We will use ROC curves and Chi-squared tests to explore the association of tool performance with child household contact IGRA positivity, to assess the ability of these tools to identify individuals with aTB who contribute to Mtb transmission.

We will compare bioaerosol status between aTB and sTB index cases and controls. Bioaerosol measurements will also be compared with tongue swab NAAT results. We will also explore their association with child IGRA positivity, to assess their performance as a surrogate for Mtb household transmission.

TB UNCONFIRMED (TB-U)COHORT STUDY (SUB-STUDY 2)

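### Excluding a child IGRA prevalence ratio of 0.50 does not show that aTB-C transmits at least half as much as sTB-C, and the stated 80% power is not power for that claim

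*Protocol*

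**What the plan says.** Protocol 5.1 sets out the role of the outcome: "We are using child IGRA positivity as a proxy measure of TB transmission". For the comparison of aTB-C with sTB-C it says "we have used the risk ratio (relative risk) as the effect estimate of interest", because the two groups of children are expected to have been exposed to the index case for a similar time. It takes a non-inferiority approach to power. The claim, put at 80% power or more for both sites and with a true ratio of 0.90 or more, reads: "demonstrate that the transmission risk with aTB-C is not less than 50% compared with that of sTB-C, assuming that the true risk ratio". The Protocol Summary repeats the claim: "demonstrate that the transmission risk with aTB-C is not less than 50% of the transmission risk of sTB-C".

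Table 3 gives the assumed IGRA positivity in per cent: "STB index HH: 40% Control HH: 20" for Indonesia and "STB index HH: 18% Control HH: 7" for South Africa.

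In 5.2 the model for this comparison contains only the aTB and sTB groups: "The marginal risk ratio will be estimated from the fitted model". Control households do not enter it. On infection acquired outside the household, 5.2 says: "This effect should be non-differential so would bias estimates towards the null". The response offered there is a sensitivity analysis in younger children.

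**The concern.** A child in an aTB-C or sTB-C household can be IGRA positive because of the index case or because of the community. The ratio of total prevalence mixes the two, and the community part pulls the ratio towards 1. Statements about relative transmission concern only the part due to the index case, so a bound of 0.50 on the mixed ratio is a weaker bound on transmission. How much weaker depends on background prevalence, which the plan itself puts at 20% and 7%.

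Section 5.1 recognises lifetime community exposure when it chooses a risk difference for the first co-primary objective. Children in aTB-C and sTB-C households share that exposure. Similar duration of contact with the index case does not remove it from the ratio.

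Section 5.1 links this comparison to policy decisions. A lower confidence limit just above 0.50 could be reported as evidence that aTB-C transmits at least half as much as sTB-C when the data show much less than that.

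**Working it through.** **Inputs (Protocol 5.1, Tables 3 and 5).** sTB prevalence ps = 0.40 (Bandung), 0.18 (KZN). Control prevalence pc = 0.20, 0.07. 150 aTB-C, 150 sTB-C and 300 control households per setting. Children per household m = 1.5 (SD 0.7), 2.5 (SD 1.6). ICC 0.30. True ratio 0.90. Lower limit of a 95% interval.

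**Design effect (DE).** 1 + (m − 1) × ICC = 1.15 (Bandung), 1.45 (KZN). Allowing for varying household size, 1 + ((CV² + 1)m − 1) × ICC = 1.25, 1.76. Effective children per TB group, 150m/DE = 196 to 180 (Bandung), 259 to 213 (KZN).

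**The plan's own figure.** SE² = (1 − pa)/(n·pa) + (1 − ps)/(n·ps); power = Φ(ln(RR/0.5)/SE − 1.96).
- Bandung, pa = 0.36, n = 196: SE = 0.129, power 99.5% (99.2% with varying household size).
- KZN, pa = 0.162, n = 259: SE = 0.194, power 85.8% (78.6%).

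The stated power of at least 80% is reproduced to within 2 points. The Bandung limits in Table 5 also reproduce (0.467, 0.546, 0.626 against 0.46, 0.55, 0.63). The KZN limits come out somewhat lower two-sided (0.39, 0.46, 0.52 against 0.43, 0.49, 0.55) and close one-sided; this does not affect the point.

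**What a ratio of 0.50 means for transmission.** Take pc as the background in TB households. Relative transmission is θ = (pa − pc)/(ps − pc). This holds whether background adds to household infection or acts independently of it, because the factor (1 − pc) cancels.
- Floor at θ = 0: pc/ps = 0.20/0.40 = 0.50 (Bandung); 0.07/0.18 = 0.39 (KZN).
- Ratio 0.50, Bandung: pa = 0.20, θ = 0/0.20 = 0%.
- Ratio 0.50, KZN: pa = 0.09, θ = 0.02/0.11 = 18%.
- Table 5 limits at true ratio 0.90: 0.63 in Bandung gives θ = (0.252 − 0.20)/0.20 = 26%; 0.55 in KZN gives θ = (0.099 − 0.07)/0.11 = 26%.

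**Range.** The Bandung contact data in the Background (52% and 57%, against 21% in neighbours) give θ at 0.50 of (0.26 − 0.21)/0.31 = 16% and (0.285 − 0.21)/0.36 = 21%. With ps = 0.40 and a background of 10%, 15% or 25%, θ is 33%, 20% or below zero. Across the KZN intervals in the Background it runs from below zero to about 40%. A ratio of 0.50 means half the transmission only if background is zero.

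**Chance of clearing 0.50 when θ is below one half (ICC 0.30, both design effects).**

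| True θ | Bandung | KZN |
|---|---|---|
| 0 | 2.5% | 0.2% |
| 0.25 | 29–31% | 5% |
| 0.40 | 61–65% | 16–19% |

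**Power for a half-transmission claim.** θ = 0.5 corresponds to a prevalence ratio of (pc + 0.5(ps − pc))/ps = 0.30/0.40 = 0.75 (Bandung) and 0.125/0.18 = 0.69 (KZN). Test pa − 0.5ps − 0.5pc > 0 at true ratio 0.90, with 2n effective control children:
- Bandung: 0.36 − 0.20 − 0.10 = 0.06; SE = 0.040; z = 1.51 (1.45 with varying household size); power 30–33%.
- KZN: 0.162 − 0.09 − 0.035 = 0.037; SE = 0.026; z = 1.40 (1.27); power 25–29%.
- At ICC 0.20: at most 34% and 32%.

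**The case against.** **No formal test is fixed.** The 0.50 appears in 5.1 as a target for the power calculation. Section 5.2 only estimates the marginal risk ratio, and the statistical analysis plan may say how its interval is to be read. A reader might infer that the protocol commits the study to declare non-inferiority at 0.50; it does not. This stands. What remains wrong is the property claimed in the Summary and 5.1.

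**The objective is a comparison of IGRA positivity, and a prevalence ratio answers it.** This also stands. The fault lies in calling the ratio transmission risk and attaching 50% to it.

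**The exact zero is fragile.** It holds only for Bandung at 40% and 20%, with control prevalence as background. A reader might infer that the bound means zero transmission in general, or that it would readily be met if aTB-C transmitted nothing. Neither follows: in KZN the bound is 18% of the excess, and with no transmission it would be met about 2.5% of the time in Bandung and 0.2% in KZN. On the plan's values, clearing 0.50 does exclude zero transmission.

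**The plan does not call the bias conservative.** It says only that it runs towards the null. The missing statement is that, for this comparison, that direction favours a non-inferiority reading.

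**Other planned work bears on background.** The aTB–control comparison, IGRA conversion, the analysis in younger children and the stage gate all help, but none rescales the 50% statement.

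**Making the excess-risk ratio the co-primary is not clearly right.** It would have 25–33% power. Reaching 80% would need roughly (2.80/1.51)² to (2.80/1.45)², about 3.5 times the households in Bandung, and (2.80/1.40)² to (2.80/1.27)², 4 to 5 times, in KZN. Controls are selected around aTB-C households only, so the sTB–control contrast is unmatched. For these reasons it is proposed below as a supporting estimate.

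**Conclusion.** The concern holds as a misstatement of what the second co-primary comparison can show. The power of at least 80% belongs to excluding a prevalence ratio of 0.50. On Table 3 that ratio represents 0% of the sTB excess in Bandung and 18% in KZN, so excluding it supports at most that some household transmission occurs. For a claim of at least half, the lower limit would have to exceed 0.75 in Bandung or 0.69 in KZN, with power of about 30–33% and 25–29% at a true ratio of 0.90.

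These figures rest on control-household prevalence being the background in TB households, on the Table 3 values and on an ICC of 0.30. The alternatives examined move the share of excess at 0.50 between below zero and about 40%. None brings it to one half, so the direction is secure and the exact zero is not.

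**What to change.** 1. In the Protocol Summary, 5.1 and Table 5, word the claim as a ratio of child IGRA prevalence and remove the statement that transmission risk is at least 50% of that of sTB-C. Beside each bound, show the zero-transmission floor (0.50 Bandung, 0.39 KZN) and the share of sTB excess it represents, with the background assumption and a range.
2. In 5.2, state that bias towards the null is anti-conservative for a non-inferiority reading of the aTB–sTB comparison.
3. Pre-specify a supporting estimate of (aTB − control)/(sTB − control) with a bootstrap or Fieller interval. Adjust the sTB–control contrast for covariates, because controls are matched to aTB-C households only. State its low power, and base any statement on relative transmission on this ratio.
4. Re-estimate the floor at the stage gate together with the other assumptions.

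The cost is rewording, a revised Table 5 and one added analysis, all from data already planned. The price is that the stated power for a half-transmission claim falls from at least 80% to about 25–33%.

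### Table 5: the South African limits do not have the stated 80% power at ICC 0.30, and the column headed as a relative reduction holds lower confidence limits for the risk ratio

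*Protocol*

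**What the plan says.** All of this is in the protocol, Section 5.1, core study.

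- **Design and claim.** For the comparison of aTB-C with sTB-C households the effect measure is the risk ratio: "therefore, we have used a non-inferiority approach for our power calculations". The conclusion reads "With 150 sTB-C and 150 aTB-C index cases, we will have at least 80% power in each setting" to show a transmission risk "not less than 50% compared with that of sTB-C, assuming that the true risk ratio (RR) is at least 0.90". Table 5 is cited in support.
- **Outcome rates.** The assumed "prevalence of IGRA positivity in children in sTB-C households is 40% in Bandung and 18% in KwaZulu Natal".
- **Household size.** The plan expects "an average of 1.5 (SD=0.7) and 2.5 (SD=1.6) children per household, respectively, in each setting".
- **Clustering.** "We have assumed an intra-cluster correlation coefficient (ICC) of 0.20-0.30 in each setting". Footnote 1 of Table 5 fixes the ICC at 0.30 for that table.
- **Table 5.** The title is "Relative reduction that can be excluded with 80% power, comparing aTB and sTB households", and the last column header likewise speaks of a relative reduction. Footnote 2, attached to that header, says the entries are lower 95% confidence limits for the risk ratio. At true ratios 0.70 / 0.80 / 0.90 the entries are 0.46 / 0.55 / 0.63 for Indonesia and 0.43 / 0.49 / 0.55 for South Africa.

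**The concern.** Two things look wrong.

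First, the six rows of Table 5 share one ICC, one confidence level, one power and one number of households, so a single formula should generate all of them. It generates the Indonesian rows but not the South African ones, and all three South African values err in the favourable direction.

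Second, the heading and the content disagree. Read as relative reductions, the entries say that the closer aTB-C is to sTB-C in truth, the larger the reduction needed before it can be excluded. That is backwards.

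These are the planning figures for a co-primary objective. Section 5.2 analyses each setting separately, so Indonesia cannot compensate for KwaZulu-Natal. The printed 0.55 also suggests more room above the 0.50 bound than the inputs give.

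**Working it through.** **Inputs**, all from Section 5.1: 150 households per group; mean children per household m = 1.5 (SD 0.7) in Bandung and 2.5 (SD 1.6) in KwaZulu-Natal; IGRA positivity in sTB-C households p1 = 0.40 and 0.18; p2 = RR × p1; ICC 0.30; two-sided 95% limit; 80% power.

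**Formulas**

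- Children per group: n = 150 × m, so 225 in Bandung and 375 in KwaZulu-Natal.
- Design effect, equal household sizes: DE = 1 + (m − 1) × ICC, so 1.15 and 1.45.
- SE² of log RR = DE × [(1 − p1)/(n p1) + (1 − p2)/(n p2)].
- Limit excluded with 80% power = RR × exp[−(1.960 + 0.842) × SE].
- Power at a printed limit L = Φ[ln(RR/L)/SE − 1.960].

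**Indonesia first.** At RR 0.70: 0.60/90 + 0.72/63 = 0.01810; times 1.15 gives SE = 0.144; limit 0.467. The three rows give 0.467 / 0.546 / 0.626 against the printed 0.46 / 0.55 / 0.63. Power at the printed limits is 83% / 79% / 79%. These rows reproduce.

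**South Africa, same formula.** At RR 0.90: 0.82/67.5 + 0.838/60.75 = 0.02594; times 1.45 gives SE = 0.194; limit = 0.90 × exp(−0.543) = 0.523. Power at the printed 0.55 is Φ(0.4925/0.194 − 1.960) = 72%.

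| True RR | Printed limit | Limit with 80% power | Power at printed limit | Design effect implied by printed limit |
|---|---|---|---|---|
| 0.70 | 0.43 | 0.388 | 64% | 0.99 |
| 0.80 | 0.49 | 0.455 | 68% | 1.09 |
| 0.90 | 0.55 | 0.523 | 72% | 1.19 |

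The implied design effect should be the same in every row and equal to 1.45. It varies, and the first row implies no clustering at all. Rounding of the printed limits does not explain the gap: taking each limit 0.005 lower gives at most 66% / 70% / 73%. Keeping the printed limits at 80% power would need about 220 / 199 / 183 households per group instead of 150.

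**Counting household-size variation.** With equal weight per child, DE = 1 + [m(1 + CV²) − 1] × ICC. For KwaZulu-Natal CV² = (1.6/2.5)² = 0.4096 and DE = 1.757. The limits become 0.365 / 0.430 / 0.495, and power at the printed limits is 56% / 60% / 64%. A beta-binomial simulation agrees (55% / 60% / 64%). For Bandung DE = 1.248 and the limits are about 0.46 / 0.54 / 0.62.

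**Other readings tried for South Africa, equal sizes**

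- ICC 0.20, the low end of the stated range: 69% / 73% / 77%.
- ICC 0.30 read on the latent logistic scale: 71% / 75% / 78%.
- One-sided 5% limit: 75% to 81%. This contradicts footnote 2 and would put the Indonesian rows at 87% to 90%.

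None reproduces all six rows.

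**Label.** The relative reduction excluded is 1 minus the limit. The printed entries correspond to 0.54 / 0.45 / 0.37 for Indonesia and 0.57 / 0.51 / 0.45 for South Africa.

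**Headline claim, KwaZulu-Natal, RR 0.90 against 0.50, ICC 0.30.** With equal sizes: Φ(0.588/0.194 − 1.960) = 86%. With SD 1.6 and equal weight per child: 79% by formula, 78% by simulation.

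**The case against.** The strongest reply is that the only conclusion drawn from Table 5 is the power against 0.50, and that this survives. A reader might infer from the SD-inflated figure that KwaZulu-Natal falls short of 80% and that its power should be restated as about 78%. The documents do not support that. The 78% to 79% figure gives every child equal weight, whereas Section 5.2 plans a logistic model with a random household intercept, which gives children in large households less weight. Weighting each household according to its size and the ICC, and assuming a shifted negative binomial for household size, brings the design effect down to about 1.59. Power is then 83% by formula and 81% by simulation. That only approximates the planned model, but it is enough to make the shortfall depend on an assumption. This part of the reply stands.

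It is also fair that footnote 2 discloses what the column holds and that the text beside the table describes the comparison correctly, so the label is a presentation fault. Section 5.1 further commits to re-estimating ICC, household size and IGRA positivity after 20% of screening and allows the sample size to change. This limits the practical harm, but it does not correct figures that misstate the current assumptions.

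Finally, nothing says that Table 5 used the household-size SD. The main error does not need it: the rows fail with equal household sizes.

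**Conclusion.** The three South African entries of Table 5 are wrong on the protocol's own inputs. They are too favourable by about 0.03 to 0.04 on the risk-ratio scale, and power at them is 64% / 68% / 72% rather than 80%, lower still if size variation is counted with equal weight per child. This rests on reading the ICC of 0.30 as applying to the binary outcome and on a two-sided 95% limit. Of the other readings tried, only the one-sided limit takes a row (RR 0.90) past 80%, and that contradicts footnote 2. The RR 0.70 row stays well below 80% under every two-sided reading tried.

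The title and column header are mislabelled, although footnoted.

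The claim of at least 80% power to exclude 0.50 in KwaZulu-Natal is not refuted. It is 86% with equal household sizes and borderline, about 78% to 83% depending on weighting, with SD 1.6. What is missing there is a statement of the assumption. The correction should be made, but it does not by itself call for a change to the design.

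**What to change.** 1. Correct the cells in one of two ways. Either replace the South African values with 0.39 / 0.46 / 0.52 (the middle value is 0.4549, so three decimals, 0.388 / 0.455 / 0.523, are safer), which matches the method behind the Indonesian rows. Or recompute all six rows by one method that counts the stated household-size SD, and say so. With equal weight per child that gives about 0.37 / 0.43 / 0.50 for South Africa (0.365 / 0.430 / 0.495) and 0.46 / 0.54 / 0.62 for Indonesia. Inflating South Africa alone would leave one table computed two ways.
2. Retitle the table and its last column along the lines of: Risk ratio that can be excluded (lower 95% limit).
3. Beside the 80% claim for the 0.50 bound, state whether household-size variation is included and with what weighting. Do not simply replace the claim with 78%.

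The cost is a table correction and one added sentence. The South African figures become slightly less favourable, and the reassessment after 20% of screening starts from a correct baseline.

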TB-UNCONFIRMED (TB-U) COHORT STUDY (SUB-STUDY 2)

A total of 1000 individuals (500 from Bandung and 500 from KwaZulu Natal) identified through the community-based screening who have chest x-rays suggestive of TB and negative baseline sputum will be followed prospectively. Based on published data that found that individuals with radiographic evidence of TB progressed to microbiologically-positive disease at an annualized rate of 10% (95% CI 6.2-13.3)⁶⁵, we anticipate 31-66 progressors to microbiologically-confirmed TB from each site.

With 50 individuals who progress and 100 who do not, we will have $\geq 80\%$ power to detect a difference of 0.50 standard deviations in mean biomarker concentrations between the two groups. If the prevalence of biomarkers in individuals who do not progress is 10-20%, we would have $\geq 80\%$ power to detect an increase to 30-40%.

STAGE GATE

We have used our best estimates of the prevalence of TB-C, prevalence of IGRA positivity, number of children per household, and value of the ICC to inform our sample size calculations, based on the available data in each setting. However, given the limited data available, there is uncertainty in these assumptions and a small change in any one of these (e.g. in household size, ICC, or the prevalence of

IGRA positivity) can have a large impact on our power. Therefore, after 20% of the population has been screened at each site (12,000 in Bandung and 6000 in KwaZulu Natal), we will assess the accuracy of the key assumptions used in our sample size calculations. Specifically, we will analyse the available data to determine the population prevalence of aTB-C, the proportion of children aged 2-14 years who are IGRA positive, average household size, and the estimated ICC. We will then use these revised estimates to further refine our power calculations for the co-primary endpoints. The results will be discussed with the funders and, if necessary, we may adjust the project sample size, budget and timelines to ensure sufficient power to address both co-primary endpoints. We will also evaluate any data available for the TB-U cohort (proportion of participants meeting the screening definition of TB-U who are confirmed aTB-C by 2 additional sputum specimens, proportion of TB-U participants who progress to TB-C) and we may adjust the TB-U cohort size to address its powering endpoint.

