We will use survival analysis methods to estimate the time to progression. The primary progression endpoint will be defined as a positive sputum test. An alternative progression endpoint will include worsening of symptoms or clinical status, radiological progression and/or starting TB treatment. Person-time will be calculated from date of entry to the TB-U cohort until the earliest of date of the progression endpoint, the last visit seen, or death. Participants who have not met the progression endpoint by the end of follow-up will be censored administratively at the date of the 12-month visit. Since we expect <15% to progress (based on published data), we will use restricted mean survival time (RMST) to estimate the average survival over follow-up. We will use linear regression to compare log-transformed plasma biomarkers between progressors and non-progressors, assuming a normal distribution, or Wilcoxon rank sum tests if data are non-normally distributed. Biomarkers that are measured as binary variables will be compared between groups using Chi-squared tests. Factors associated with time to progression will be explored using Cox regression.

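### TB-U cohort: 50 progressors and 100 non-progressors give about 73-74% power, not at least 80%, for a rise in biomarker prevalence from 20% to 40%

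*Protocol*

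**What the plan says.** Protocol section 5.1, under the TB-U cohort study, plans to follow 500 people per site. It expects 31-66 progressors per site, from a published annualised rate of 10% (95% CI 6.2-13.3). It then makes two power statements on one pair of group sizes: "With 50 individuals who progress and 100 who do not, we will have" at least 80% "power to detect a difference of 0.50 standard deviations in mean biomarker concentrations between the two groups". For binary markers it continues "If the prevalence of biomarkers in individuals who do not progress is 10-20%, we would have" at least 80% "power to detect an increase to 30-40" per cent. The Sample size row of the Protocol Summary repeats both statements.

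Section 5.2 names the test: "Biomarkers that are measured as binary variables will be compared between groups using Chi-squared tests". It also rules out pooling the two countries: "The analyses for each endpoint will be conducted separately for each setting". Neither place gives alpha or sidedness for this calculation.

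**The concern.** The binary statement gives one power guarantee for a range of starting prevalences. With a fixed 20-point rise and fixed group sizes, power falls as the starting prevalence moves from 10% towards 20%, because the binomial variance grows. A guarantee that is met at 10% can therefore fail at 20%.

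The biomarker sentences are the only power statements given for this cohort. The stage-gate text in section 5.1 allows the cohort size to be adjusted. A reader judging what 50 and 100 can deliver would take the upper end of the range as secured when it is not.

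**Working it through.** **Inputs.**
- Group sizes: n1 = 50 progressors and n0 = 100 non-progressors (section 5.1).
- Prevalences: the ranges 10-20% and 30-40% are read as matched 20-point rises, 10% to 30% and 20% to 40%. The crossed pair 20% to 30% has only about 28% power, so matched pairs are the sensible reading of a claim over the whole range.
- Test: Chi-squared (section 5.2).
- Alpha: two-sided 0.05, which is my assumption.

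**Checking the alpha convention on the companion claim.** For a 0.50 SD difference the standardised effect is 0.50 / √(1/50 + 1/100) = 2.887. Normal-approximation power is Φ(2.887 − 1.960) = 82.3%, and the t-test gives 81.8%. The companion claim reproduces at two-sided 0.05.

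**Formula for the binary claim.** Power = Φ[(|p1 − p0| − 1.960 × SE0) / SE1], where
- p̄ = (n0·p0 + n1·p1) / (n0 + n1)
- SE0 = √[p̄(1 − p̄)(1/n0 + 1/n1)]
- SE1 = √[p0(1 − p0)/n0 + p1(1 − p1)/n1]

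**20% to 40%.** p̄ = (20 + 20)/150 = 0.2667. SE0 = √(0.2667 × 0.7333 × 0.03) = 0.0766. SE1 = √(0.0016 + 0.0048) = 0.0800. Power = Φ[(0.20 − 0.1501)/0.0800] = Φ(0.623) = 73.4%.

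**10% to 30%.** p̄ = 0.1667, SE0 = 0.0645, SE1 = 0.0714. Power = Φ(1.029) = 84.8%.

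The last column enumerates the uncorrected Chi-squared test exactly over both binomial distributions.

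| Rise | Progressors / non-progressors | Formula | Exact |
|---|---|---|---|
| 10% to 30% | 50 / 100 | 84.8% | 86.4% |
| 15% to 35% | 50 / 100 | 78.5% | 79.4% |
| 20% to 40% | 50 / 100 | 73.4% | 73.9% |
| 20% to 42% | 50 / 100 | 80.3% | 80.9% |
| 20% to 40% | 50 / 170 | 80.2% | 80.5% |
| 20% to 40% | 50 / 450 | 86.4% | 86.6% |
| 20% to 40% | 31 / 100 | 60.7% | 61.1% |
| 20% to 40% | 31 / 469 | 71.6% | 71.4% |

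**Choice of formula.** For 20% to 40% with 50 and 100, the other two-sided 0.05 variants are lower still: unpooled 70.5%, arcsine 72.3%, likelihood-ratio 72.7%, Fisher 69.4%, and continuity-corrected about 67%. None comes within 6 points of 80%. Keeping the 1:2 ratio, 80% would need about 60 progressors and 119 non-progressors.

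**The case against.** **One-sided testing.** A one-sided 5% test would give about 82% for 20% to 40%. The Protocol states no such test, the planned Chi-squared test is two-sided, and the 0.50 SD claim reproduces at two-sided 0.05. This does not rescue the figure.

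**Pooling the sites.** Doubling both groups to 100 and 200 would give about 95%, but the text specifies 50 and 100, and section 5.2 analyses each setting separately.

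**Comparators left out.** A reader might infer from the 50 and 100 that the analysis discards most non-progressors. The documents do not support that. Section 5.2 compares progressors with non-progressors and sets no cap at 100; the 100 appears only in the power statements. If all 450 at a site are analysed, power for 20% to 40% is 86-87%. This objection stands: the fault is in the stated figure, and an under-powered analysis is not established.

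**Basis of the cohort size.** A reader might also infer that this comparison sets the cohort size. The Summary presents 500 per setting as the number expected from screening. The stage-gate text refers to a powering endpoint without naming it, and the TB-U inputs it lists for review are confirmation on further sputa and progression, not biomarker prevalence.

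**Fifty progressors.** It is tempting to call 50 optimistic because 31 is possible. The statement is expressly conditional on 50, which is the central estimate (10% of 500), and the 31-66 range is disclosed in the paragraph before. Power at 31 is useful information, but its absence is not an error.

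**Size of the error.** Two percentage points in one detectable prevalence is small, and the comparison is secondary. That bears on priority, not on whether the figure is right.

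**Conclusion.** The stated power is wrong at the upper end of its own range. With 50 progressors and 100 non-progressors, power is 73-74% for 20% to 40%, a shortfall of 6 to 7 points, and about 79% at the midpoint. The 10% to 30% end and the 0.50 SD claim are sound. The result rests on two-sided 0.05, on matched 20-point rises, and on the uncorrected Chi-squared test analysed by setting.

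The reach is limited to one secondary comparison in sub-study 2. Neither co-primary objective is touched. The correction is nevertheless worth making, because the Protocol states the figure twice as a guarantee.

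**What to change.** In both the Protocol Summary and section 5.1, state alpha and sidedness for the calculation. Then do one of the following:

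- Keep 50 and 100, and restate the upper end as a rise from 20% to about 42%.
- Keep the rise from 20% to 40%, and base the calculation on about 170 or more non-progressors, or on all 450, where the assay is run on all participants.

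Optionally, add the power at 31 progressors: 61% against 100 non-progressors and about 71% against all 469. This shows that a larger comparator group restores 80% only if progressors are near the central estimate.

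The first option costs only wording. The second needs no extra participants. For cell-free DNA and T cell activation, Table 7 (Appendix C) already schedules the blood sample at every cohort visit. It does not schedule transcriptional assays, which section 3.6 describes only as a possible use of stored samples. For those markers a larger comparator group could mean extra laboratory cost, and the first option may fit better.
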